In [Table 1](#), the number of patients treated is indicated in the columns and the number of patients who experienced a DLT is indicated in the rows. Dosing decisions include escalate to the next higher dose (E), stay at the current dose (S), de-escalate to the next lower dose (D), and de-escalate to a lower dose and never test this dose again (i.e., unacceptably toxic dose; DU). During dose escalation, a minimum of 3 patients are required at each dose. Depending on accrual rate and occurrence of DLTs, 3, 4, 5 or 6 patients may be enrolled at each new dose until the last of those patients completes the Cycle 1 DLT assessment period. For example, the dose escalation rules will proceed as follows if 3 patients are enrolled: if 0 of the first 3 patients at a given dose level develops a DLT, then the dose can be escalated to the next level without further expansion. If 1 of the first 3 patients at a given dose level develops a DLT, no more than an additional 3 patients should be enrolled at this dose level until additional DLT data are available since this dose would be considered unacceptably toxic if all 3 of the additional patients experience a DLT (i.e., 4 of 6 patients). If 2 of the first 3 patients at a given dose level develop a DLT, the dose will be de-escalated to the next lower level. If 3 of the first 3 patients at a given dose level develop a DLT, this dose will be considered unacceptably toxic (i.e., the dose will be de-escalated and never re-escalated to that dose again). The same principle will be applied whether 3, 4, 5 or 6 patients are enrolled in the same dose cohort according to [Table 1](#).

Based on the mTPI design, the number of patients who are enrolled at a dose, but are not yet fully evaluable for DLT assessment, may not exceed the number of remaining patients who are at risk of developing a DLT before the dose would be considered unacceptably toxic (denoted as DU in [Table 1](#)). To determine how many more patients can be enrolled at a dose level, one can count steps in a diagonal direction (down and to the right) from the current cell to the first cell marked DU. In total, 3 to 14 patients may be enrolled at a given dose level.

Dose escalation and confirmation will end after 14 patients have been treated at any of the selected doses. The pool-adjacent-violators-algorithm (Ji et al 2013) will be used to estimate the

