10.1. Populations for Analysis

The following populations will be defined:

- The safety population includes participants who were enrolled, allocated to treatment, and received at least one dose of investigational product.
- The efficacy population includes participants who received study drug and had an on-treatment response assessment (including “Not Evaluable”) or who discontinued study before any response assessment was performed due to disease progression.
- The PK/PD population includes participants who received study drug and had at least one PK or PD assessment.

Additional populations may be defined in the SAP, as required.

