For records with a missing procedure date, the following procedure will be employed for use in determining whether the procedure is prior or concomitant:

- Procedure dates with a missing day and non-missing month will be assumed to occur on the first day of the non-missing month, except for

- procedures occurring in the month of first dosing, in which case the date will be the date of first dosing.
- Procedure dates with missing day and month will be assumed to occur on the first day of the non-missing year (i.e., January 1), except for procedures occurring in the year of first dosing, in which case the date will be the date of first dosing.

For records with a missing disease progression date from prior therapy, the following procedure will be employed for use in analyzing time to event endpoints:

- If the disease progression date is completely missing OR only the year is available, set as missing.
- If both year and month of disease progression date from are available and only day is missing, the date of disease progression will be imputed by the last day of the month.

For records with a partial death date, the following procedure will be employed for use in deriving time to event variables.

- The death date will be imputed by the earliest possible date that is not contradicting with any other available data in the database.

All other data will be reported as they are collected. No imputation methods will be used to replace missing data unless otherwise stated in this document.

D. Interim Analyses

This is a single-arm, open-label study, so interim analyses may be performed as the study progresses.

Details of analysis will follow each section described in this SAP, may including the following components:

- Disposition
- Protocol deviations
- Baseline characteristics: demographics, disease history, medical history, concomitant medication/procedure
- Key components from efficacy analysis
- Key components from safety analysis
- PK and pharmacodynamic data (as available)

E. Analysis Populations

1. Safety Population

The safety population includes participants who were enrolled, allocated to treatment, and received at least one dose of investigational product.

2. Efficacy Population

The efficacy population includes participants who received study drug and had an on-treatment response assessment (including “Not Evaluable”) or who discontinued study before any response assessment performed due to disease progression.

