Patients’ best overall response will be selected based on the overall response order (CR, PR, SD, PD, NE for RECIST; CR, PR, SD, PD, IR1, IR2, IR3 for LYRIC) through the study. Objective Response Rate (ORR), defined as the proportion of patients’ overall response achieving a PR or CR at any time on the study, will be summarized descriptively by arm and cohort. In addition, an exact 90% confidence interval (CI) will be presented for RP2D cohort in Arm 2. Note that the definition of the Efficacy Population includes all treated patients who have an on-treatment response assessment or who discontinued study early due to disease progression; therefore, all Efficacy Population patients will be included in the denominators for percentage even if the patient had a Not Evaluable response. The best overall response and objective response rate will be summarized separately for each assessment method (RECIST, iRECIST, or LYRIC).

Similarly, the proportion of patients with a PR and the proportion of patients with a CR at any time during the study will be summarized as part of the best

overall response. The sum of diameters and change from baseline will also be summarized, by arm and cohort at each assessment visit.

All overall tumor and lymphoma response data will be presented in patient listings.

3. Determination of Time to Event Endpoints

Below is a list of events definitions for the solid tumor patients with a confirmed response according to RECIST v1.1 and iRECIST, and lymphoma patients with response according to LYRIC. The number of events and the number of censored patients will be summarized. The median time to event (reported in days) and the 25th and 75th percentiles on the time to event for each arm and cohort will be summarized using Kaplan-Meier estimates. Progression-Free Survival graphs will also be provided.

When calculating the endpoint that involve PD diagnosis date, such as time to progression or progression free survival, below rules will apply to account for the repeated PD response assessment per iRECIST:

- When a patient has disease progression per RECIST, if the repeated assessment confirmed as disease progression according to iRECIST criteria, the first PD date will be used in the endpoint calculation.

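### The ORR denominator leaves out treated patients who have no on-treatment response assessment for a reason other than progression, so ORR can only be biased upward

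*SAP*

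**What the plan says.** SAP V.E.2 admits a treated patient to the Efficacy Population by two routes. The first is an on-treatment response assessment, where a Not Evaluable (NE) result is enough. The second is for a patient without any assessment, "who discontinued study before any response assessment performed due to disease progression". Protocol 10.1 has the same rule ("who discontinued study before any response assessment was performed due to disease progression").

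SAP VII.A.2 makes this set the ORR denominator and comments on one consequence only: "all Efficacy Population patients will be included in the denominators for percentage even if the patient had a Not Evaluable response". It adds that "an exact 90% confidence interval (CI) will be presented for RP2D cohort in Arm 2". ORR is summarised by arm and cohort, and separately for each set of response criteria. In SAP Appendix 5, Tables 11 and 12 (tumor and lymphoma response) are on the Efficacy Population only.

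The Safety Population (SAP V.E.1) is wider: it needs enrolment, allocation and that the patient "received at least one dose of investigational product". SAP V.C states that missing data are not imputed unless the SAP says so, and it says nothing of the kind for ORR.

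On scan timing, Protocol 7.3 schedules imaging at screening, at the end of each even-numbered cycle, and at the end-of-treatment (EOT) visit unless there was imaging in the preceding 8 weeks. SAP IV.B repeats that waiver. SAP VII.A.1 lists the EOT assessment without it.

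**The concern.** The rule treats similar patients differently. A patient with an uninformative scan (NE) stays in the denominator. So does a patient with no scan who stopped for progression. A patient with no scan who died of another cause, or who withdrew consent for follow-up, is removed. All three are non-responders on any reading, but only the third kind disappears.

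Early stops are foreseeable. Cycles last 21 days, so the first scheduled on-study scan is at about Day 42. The protocol has several routes off treatment before then, for example missed Cycle 1 doses (4.3.1) or the need for a Cycle 1 dose reduction (4.3.2.1).

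What is at stake is the reported ORR in every cohort and the one interval estimate of activity in the plan, at the Arm 2 RP2D. A reader would take that estimate to describe patients treated with the combination, when it describes a subset selected partly on what happened after dosing.

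**Working it through.** **Stated figures.** The plan gives no ORR assumption, CI width or power to reproduce. Its only sample size, about 70, is consistent with 7 × (3+1) + 5 × (3+1) + 20 = 68. That does not bear on this point.

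**Who falls through both routes.**
- Non-progression death before any assessment: the EOT scan cannot help.
- Withdrawal of consent for follow-up before any assessment: Protocol 8.2 releases the patient from the EOT visit.
- Other early stops, including toxicity: dropped only if the EOT scan is waived or not counted as on-treatment, and no NE is recorded.

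**How far the waiver reaches.** Screening may be 28 days before the first dose. A patient whose last injection is on Day 15 has an EOT visit within 14 days, so by Day 29, which is 28 days after Day 1. The gap from the screening scan is at most 28 + 28 = 56 days, exactly 8 weeks. Read literally, a screening scan can therefore waive the EOT scan after a Cycle 1 stop; visit windows could add a day or so. The SAP does not say whether an EOT scan counts as on-treatment.

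**Size of the RP2D cohort.** Protocol 4.2.3 says "3 to 14 patients may be enrolled at a given dose level" and allows up to 20 additional patients at the RP2D. A full expansion gives N = 3 + 20 = 23 to 14 + 20 = 34.

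**Formula.** With N treated, x responders and d dropped, all-treated ORR = x/N and planned ORR = x/(N-d). The ratio is N/(N-d). Dropped patients have no assessment, so x is the same in both.

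**Results.** Intervals are Clopper-Pearson with 5% per tail (two-sided assumed). The values of x and d are assumptions. All patients are taken to fall under one set of response criteria; a mix of solid tumors and lymphoma would make each denominator smaller.

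| N | x | d | ORR | Exact 90% CI | N/(N-d) |
|---|---|---|---|---|---|
| 23 | 4 | 0 | 4/23 = 17.4% | 6.2-35.5% | 1.00 |
| 23 | 4 | 1 | 4/22 = 18.2% | 6.5-36.9% | 1.05 |
| 23 | 4 | 3 | 4/20 = 20.0% | 7.1-40.1% | 1.15 |
| 34 | 6 | 0 | 6/34 = 17.6% | 8.0-31.9% | 1.00 |
| 34 | 6 | 2 | 6/32 = 18.8% | 8.5-33.7% | 1.06 |
| 34 | 6 | 5 | 6/29 = 20.7% | 9.4-36.8% | 1.17 |

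With no responders the ORR is 0% either way and only the upper limit moves: 12.2% for 0/23 against 13.9% for 0/20.

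A three-patient dose-finding cohort is more sensitive. One responder with one patient dropped turns 1/3 = 33% into 1/2 = 50%, although no CI is planned there.

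**The case against.** The strongest reply is that few patients are really lost. Imaging is scheduled at EOT. Protocol 8.2 requires the EOT visit after withdrawal unless consent for follow-up is withdrawn. Patients with a non-fatal DLT stay on study for safety evaluation (SAP VIII.B). Protocol Appendix 1 classes a patient with no imaging at a time point as not evaluable at that time point, and NE patients stay in the denominator. The rule is also prespecified and visible: disposition with reasons is tabulated, and the response listings (19 and 24) use the Safety Population, so an all-treated ORR could be rebuilt.

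Much of this stands, and it rules out three stronger readings.

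- A reader might infer that everyone who stops for toxicity before Day 42 leaves the denominator. The documents do not support that, because the EOT scan or an NE entry can retain such a patient. Retention is not assured either. The waiver can remove the scan, and V.E.2 requires an on-treatment assessment, so whether an unscanned EOT visit yields a qualifying NE is arguable.
- A reader might infer that ORR is inflated most at the highest doses and distorts a comparison between cohorts. The plan makes no such comparison. Efficacy is descriptive, escalation rests on DLTs, and the CI is for one cohort only. A dose gradient would need dropped patients to become more frequent with dose, and the documents give no figure for that.
- A reader might take the RP2D cohort as 20 patients. The 20 are additional to those from dose finding, so a smaller N overstates the effect of each dropped patient if the expansion is full.

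No part of the reply covers non-progression deaths or withdrawn consent, and no planned table adds those patients back.

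**Conclusion.** The point holds in this limited form. The stated rule can move ORR in one direction only, and does so as soon as there is one responder and one dropped patient.

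Across the examples for a full RP2D cohort, with 1 to 5 dropped, ORR rises by about 1 to 3 percentage points and the upper 90% limit by about 1 to 5. The all-treated intervals are themselves about 24 to 29 points wide. The size rests on assumed responder and dropout counts, a full expansion, and a single set of response criteria. If nobody is dropped there is no effect.

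ORR is a secondary, descriptive endpoint with no threshold attached, so no error rate, escalation decision or RP2D rule changes. It is a should-fix reporting matter, worth settling before database lock.

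**What to change.** In SAP VII.A.2 and Tables 11 and 12, make the Safety Population, split by the applicable response criteria, the denominator for ORR and its exact 90% CI. Count treated patients with no response assessment as non-responders. Keep the Efficacy Population ORR as a supportive row, and state for that row whether an EOT scan counts as on-treatment and when a missing scan is recorded as NE.

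A SAP revision may be enough: Protocol 10.3 names no ORR denominator, and Protocol 10.1 lets the SAP define additional populations. The cost is some wording, one extra row per table, and a slightly lower reported ORR if anyone is dropped.

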4.4.1. Adverse Events Associated with SYNB1891

Guidelines for the management of patients who experience AEs considered to be potentially associated with SYNB1891 are provided in [Table 2](#).

Table 2: Toxicity Management for Adverse Events Considered Potentially Associated with SYNB1891

Event	NCI CTCAE Grade	Recommended Medical Management	Premedication and Subsequent Dosing
Cytokine release syndrome (may include associated AEs, e.g., fever, tachypnea, headache, tachycardia, hypotension, rash, hypoxia)	Grade 1 Fever with or without constitutional symptoms	Increase vital sign and oxygen saturation monitoring as medically indicated until the patient is deemed medically stable in the opinion of the Investigator.	Administer as planned
	Grade 2 Hypotension responding to fluids; hypoxia responding to < 40% oxygen	Increase vital sign and oxygen saturation monitoring as medically indicated until the patient is deemed medically stable in the opinion of the Investigator. Additional appropriate therapy may include, but is not limited to: IV fluids NSAIDs Acetaminophen Narcotics Oxygen Evaluate for infectious etiologies and treat neutropenia if present.	Patient may be premedicated 1.5 hours (\pm 30 minutes) prior to study treatment administration with oral acetaminophen (500 to 1000 mg) or equivalent dose of antipyretics.
	Grade 3 Hypotension managed with one pressor; hypoxia requiring \geq 40% oxygen	Appropriate therapy may include, but is not limited to: IV fluids NSAIDs Acetaminophen Narcotics Oxygen Pressors Corticosteroids Anti-IL6 (e.g., tocilizumab) Empiric antibiotics Monitor patients closely; consider an intensive care setting	Discuss with the Sponsor prior to the resumption of study treatment. Upon approval by the Sponsor, resume SYNB1891 at a reduced dose upon AE resolution to baseline or Grade 1. Patient may be premedicated 1.5 hours (\pm 30 minutes) prior to study treatment administration with oral acetaminophen (500 to 1000 mg) or equivalent dose of antipyretics.

Event	NCI CTCAE Grade	Recommended Medical Management	Premedication and Subsequent Dosing
	Grade 4 Life-threatening consequences; urgent intervention indicated	
Appropriate therapy may include, but is not limited to:
 
 IV fluids NSAIDs Acetaminophen Narcotics Oxygen Pressors Corticosteroids Anti-IL6 (e.g., tocilizumab) Empiric antibiotics 
Monitor patients closely; consider an intensive care setting.
	Permanently discontinue study treatment.

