7.2.5. Clinical Laboratory Measurements

Clinical laboratory tests will be performed (predose unless otherwise specified) at the time points indicated in [Table 19](#) and [Table 20](#). Baseline laboratory measurements do not need to be repeated if screening measurements were performed within 3 days prior to Cycle 1 Day 1.

Screening for HIV and hepatitis B and C will also be performed prior to study dosing. Serum pregnancy testing will be performed at screening, with urine pregnancy testing performed at subsequent time points (see [Table 19](#) and [Table 20](#)).

Screening results will be assessed by the Investigator for inclusion of patients in the study. Additionally, unscheduled clinical laboratory tests can be obtained at any time during the study

at the Investigator's discretion. The diagnosis corresponding to any clinically significant abnormality, or abnormality requiring treatment/intervention, must be recorded as an AE.

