- Trial Day 1 of Cycle 1 is defined as the day on which the first dose of SYNB1891 is administered. Study days after trial day 1 will be calculated as the difference between the date of interest and the first date of dosing of study medication plus 1 day. The generalized calculation algorithm for relative day: STUDY DAY = [(TARGET DATE – DSTART) + 1 where DSTART = the start day of study drug].
- For dates of interest before the first date of dosing of study medication, the study day will be calculated as: STUDY DAY = TARGET DATE – DSTART. Negative study days are reflective of observations obtained

prior to first study drug administration. Note: Partial date for the first study drug is not imputed in general. All effort should be tried to avoid incomplete study drug start date.

- Age (years) at informed consent will be calculated as: (Date of informed consent – date of birth+1)/365.25 and then truncated to an integer. In case of partial birth date: impute missing day as 15th of the month; impute missing month as July; set missing age for missing year.
- Duration will be calculated by the difference of start and stop date + 1. AE duration (days) = AE end date – AE start date +1; study drug exposure duration (weeks) = (date of the last dose – date of the first dose + 1)/7.
- Time since disease diagnosis (months) will be calculated as (Informed Consent Date – Diagnosis Date +1)/ 30.4167.
- The time since an event will be calculated as date of event minus reference date. The specific censoring rules on the endpoint will follow section VII.
- The following conversion factors will be used to convert days to months or years:
 - 1 month = 30.4167 days
 - 1 week = 7 days
 - 1 year = 365.25 days
- Multiple Assessments for the Same Assessment Time Point

In the case of multiple observations (e.g. scheduled vs. unscheduled) at a specific visit, the first non-missing measurement will be used for analysis, unless multiple study assessments are expected (e.g., pre-dose vs post-dose). When multiple study assessments are expected, the first non-missing measurement for the visit and assessment time point will be used for analysis.

VI. Subject Accountability

A. Disposition

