Vital signs (systolic blood pressure, diastolic blood pressure, body temperature, pulse, and pulse oximetry) will be summarized with continuous descriptive statistics at screening, on Cycle 1 Day 1 (predose and 30 minutes, 1 hour, 2 hours, 3 hours, 6 hours, and 24 hours postdose), on all study treatment days (predose and 30 minutes, 1 hour, 2 hours, 3 hours, and 6 hours postdose), at EOT/Early Termination and Safety Follow up.

F. Physical Examination

Complete physical examinations will be performed at screening and Baseline, with symptom-directed physical examinations performed at subsequent time points (see Appendix 3). As a part of the physical examination and prior to each dose, a photograph of the visible injected and/or noninjected lesion(s) should be taken at the discretion of the Investigator. No information from the photo will be included into the analysis. A listing of patients' Physical Examination completion status will be provided.

G. Electrocardiograms

Semi-supine single 12-lead ECGs will be performed at screening and reviewed locally. An overall interpretation of the ECG results will be made and QT, corrected by Fridericia's formula (QTcF), intervals will be listed.

H. Multi-gated Acquisition Scan or Echocardiogram

MUGA or ECHO will be performed within 6 months prior to the first dose of study treatment provided the patient has not received any potential cardiotoxic agents in the intervening period. If potential cardiotoxic agents have been administered within 6 months, patients must undergo a MUGA/ECHO during the

screening period. Left Ventricular Ejection Fraction and an overall interpretation will be listed.

Assessments performed at screening visit, Virology (hepatitis B, C and HIV), ECGs, MUGA/ECHO, Urinalysis will be listed by patient. Clinical laboratory results, vital sign and Physical examination will be listed by patient and summarized by Arm, dose and visit in the Safety population. Summaries of baseline values and changes from baseline will be presented by dose level for each assessment time point. Shift tables summarizing the counts and percentages of patients who were normal at baseline, but who became abnormal subsequently, will also be displayed.

IX. Pharmacodynamics and Pharmacokinetics

PK and PD analysis may be reported in a separate report.

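### The first-value rule can leave a later, worse same-visit reading out of the laboratory and vital-sign summary and shift tables, and the SAP plans no worst-post-baseline display

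*SAP*

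**What the plan says.** **The selection rule.** SAP section V.F, under the item on multiple assessments at one time point, says: "In the case of multiple observations (e.g. scheduled vs. unscheduled) at a specific visit, the first non-missing measurement will be used for analysis". It makes an exception for planned repeats such as predose and postdose readings: "When multiple study assessments are expected, the first non-missing measurement for the visit and assessment time point will be used for analysis".

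**The tables it feeds.** SAP section VIII.E summarizes vital signs "on all study treatment days (predose and 30 minutes, 1 hour, 2 hours, 3 hours, and 6 hours postdose", with a 24-hour reading added on Cycle 1 Day 1. The closing paragraph of SAP section VIII.H says: "Clinical laboratory results, vital sign and Physical examination will be listed by patient and summarized by Arm, dose and visit in the Safety population". It adds: "Shift tables summarizing the counts and percentages of patients who were normal at baseline, but who became abnormal subsequently, will also be displayed". In Appendix 5, the only laboratory and vital-sign tables are the mean-change Tables 44 to 47.

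**Extra readings are foreseen.** For cytokine release syndrome, Protocol section 4.4.1 (Table 2) tells sites: "Increase vital sign and oxygen saturation monitoring as medically indicated until the patient is deemed medically stable". Protocol section 7.2.5 says that "unscheduled clinical laboratory tests can be obtained at any time during the study", and Protocol section 7.2.3 allows vital signs beyond the schedule when the clinical picture calls for them.

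**Grading.** Protocol section 10.2 commits to grading laboratory abnormalities, as well as AEs, by CTCAE version 5.0.

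**The concern.** Taking the first value is a reasonable way to get one number per patient per visit for a table of means. It is a poor way to decide whether a patient ever became abnormal. Many extra readings in a safety study are taken because something is going wrong, and they come after the routine one. If the routine reading was normal and the repeat was not, the rule keeps the normal value. The affected tables are the ones a reader would use to see, by dose, how far temperature, blood pressure, oxygen saturation, transaminases or blood counts moved in a first-in-human study of an agent whose named risks include cytokine release syndrome and systemic infection. Cohorts start at 3 patients, so a single omitted reading shows up as a large change in a percentage.

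**Working it through.** The plan states no figure to reproduce here. The check sets the rule against each planned output and then sizes one omitted reading.

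**1. Does the rule reach the shift tables?** It is a general convention in SAP section V.F, with scheduled versus unscheduled as its own example. SAP section VIII.H gives no separate rule for the shift tables. It does not say that they use the worst value, and it does not define what counts as subsequent. On the text as written, the first-value rule governs them.

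**2. Effect of reading order.** Take two readings in one patient at the same visit or time point:

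| First reading | Later reading | Kept | Counted as abnormal? | Any abnormal reading? |
|---|---|---|---|---|
| Normal | Abnormal | Normal | No | Yes |
| Abnormal | Normal | Abnormal | Yes | Yes |
| Abnormal | More abnormal | Less extreme value | Yes | Yes, but the peak is lost |
| Normal | Normal | Normal | No | No |

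Compared with a count of patients who had any abnormal reading, the first-value count is equal or lower, never higher. It is lower only in the first row, and across visits only if the patient has no abnormal selected value elsewhere. By-visit means can move either way.

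The minimum and maximum listed among the descriptive statistics in SAP section V.F do not recover a lost reading, because they are taken across the values already selected. The rule can also let an earlier unscheduled value displace the scheduled one.

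**3. Output by output.**

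- Laboratory by-visit summaries and shift tables: a later repeat at the same visit is excluded. The concern holds.
- Vital-sign summaries and shift tables: a second reading at the same time point is excluded. The scheduled readings at 30 minutes and 1, 2, 3 and 6 hours (and 24 hours on Cycle 1 Day 1) are each kept. The concern holds only for repeats outside that schedule.
- AE, Grade 3 or higher, AESI and maximum-severity tables: these are built from AE records and take the highest grade per patient and event (SAP section VIII.C). Not affected.
- DLT table: built from AEs and SAEs in Cycle 1 (SAP section VIII.B). Not affected.
- Listings: all recorded data are listed (SAP section V.F), including Listings 30, 31 and 33 and a separate Listing 43 for unscheduled assessments. Not affected.

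**4. Readings between visits.** The rule speaks of several values at one visit. After every dose other than Cycle 1 Day 1, scheduled vital signs stop at 6 hours. A later unscheduled reading, or a laboratory draw between visits, belongs to no scheduled row. The SAP does not say whether it enters the shift tables.

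**5. Grading.** Protocol section 10.2 promises graded laboratory abnormalities. The SAP grades AEs but plans no laboratory table by maximum grade. The shift tables promised in SAP section VIII.H are also missing from the Appendix 5 table list.

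**6. Size of one omitted patient.** The change in a cohort's percentage is 1/n. Protocol section 4.2.3 allows 3 to 14 patients per dose level:

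- n = 3: 1/3 = 33.3%, shown as 0/3 = 0%
- n = 6: 1/6 = 16.7%, shown as 0%
- n = 14: 1/14 = 7.1%, shown as 0%

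These are illustrations. The documents do not say how often the first-row pattern will occur.

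**The case against.** The strongest reply is that nothing important can be lost. Protocol section 7.2.5 requires the diagnosis behind a clinically significant or treated laboratory abnormality to be recorded as an AE, and Protocol section 9.6 adds values that change dosing. AE tables use the highest grade. Cytokine release syndrome is an AESI with its own table. Dose decisions rest on DLTs and on the Safety Review Committee's review of all available safety data, not on a shift table. With 3 patients per cohort, a reader can go through the listings. All of this stands. A reader might infer that worse values vanish from every safety table or could mislead escalation, and the documents do not support that.

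It does not settle the matter, because the AE route depends on judgement. DLT item 4 in Protocol section 4.2.4 excepts some reversible or clinically nonsignificant laboratory abnormalities, including liver function tests. A transient transaminase rise may therefore properly be neither an AE nor a DLT, and the laboratory table is then its only tabulated record. AE grades also do not show the peak or lowest reading.

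A second reply is that the order often runs the other way. Protocol section 9.6 asks for concerning values to be repeated, and dosing-day laboratory criteria (Protocol section 7.2.5.1) can also prompt repeats. The abnormal value then comes first and is kept. That is right, so the undercount is a possibility and not a certainty. It does not make clock order a sound basis for a count of patients who became abnormal.

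A reader might also try to size the loss from the 7-day spacing of Cycle 1 laboratory visits. That spacing describes how often the schedule samples, not what this rule removes, so it gives no estimate here.

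**Conclusion.** The point holds for a limited set of outputs: the laboratory and vital-sign by-visit summaries and the normal-to-abnormal shift tables. In these, a later, worse reading at the same visit or time point is left out, so counts of patients who became abnormal can be too low. The change is one patient's share of the cohort, 33.3 percentage points at n = 3 and 7.1 at n = 14. This rests on three assumptions: that the shift tables use the values selected under SAP section V.F, that the worse reading comes second, and that it is the patient's only abnormal one.

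Two gaps go with it. The treatment of readings between visits is undefined, and the laboratory grading promised in Protocol section 10.2 has no planned table. The primary endpoint and the dose-finding decisions are not at issue. This is a cheap improvement to the safety displays.

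**What to change.** - Restrict the first-value rule in SAP section V.F to the by-visit mean-change tables.
- State in SAP section VIII that laboratory and vital-sign shift tables use each patient's worst post-baseline value, in each relevant direction, from all scheduled and unscheduled readings, including those between visits. Present them for Cycle 1 and for the whole treatment period, by arm and dose cohort.
- Add a table of maximum post-baseline CTCAE grade for laboratory parameters, to meet Protocol section 10.2.
- List the shift and grade tables in Appendix 5.

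The cost is a few sentences in the SAP and slightly more programming on data already planned for the listings. No new assessment is needed. Reported abnormality rates will be slightly higher. A spurious reading followed by a normal repeat will count as abnormal, as it already does when it comes first; the listings allow such cases to be identified.
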